5.13 Treatment-Emergent Adverse Events (TEAEs)

TEAEs are those which first occur or increase in severity or relationship to study drug after the first dose of study drug through the Post-dose Follow-up (28 ± 3 days after end of treatment). In reality all AEs which change in severity or relationship to study drug are assigned a new start date and captured as a new record. Should the day of the AE be "unknown" and the AE in question occurs in the same month or a following month as the date of first dose, the AE will be considered treatment emergent. Should the month of the AE be "unknown" and the AE in question occurs in the same year or a following year as the date of first dose, the AE will be considered treatment emergent. Should the start date be missing then the AE will be considered treatment emergent.

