draw (hematology only) at Weeks 28, 32, 34, 40, 44 and 68. The Safety Follow-Up Visit will occur 28 ± 3 days after the patient's last open-label dose of tozadenant. Patients who received tozadenant during Part A will continue on open-label tozadenant and those who received placebo will initiate open-label tozadenant. Neither the patient nor the investigator will be unblinded to the treatment received during Part A unless required for safety purposes as determined by the investigator and agreed to by the Sponsor. Upon starting Part B, patients will receive open-label tozadenant at a dose of 120 mg BID. Adjustments to the open-label tozadenant dose are allowed starting at Week 26 and at subsequent visits. Doses of 60 or 120 mg BID are permitted; the investigator may adjust a patient's dose to either level as clinically indicated. Because the information entered in the Interactive Response System (IXRS) will be used to manage the tozadenant inventory at each study site, timely entries into the IXRS will be important.

During Part B, patients' concomitant anti-PD medications may be adjusted as needed under the investigator's supervision (see **Section 5.9.1**). The optimal dose of open-label tozadenant for each patient will be defined following discussion between the patient and the investigator, taking into account the potential for improvement of disease symptoms and the tolerability profile.

During Part B, Unscheduled Visits can be arranged as considered necessary by the investigator (see Section 6.2.34). In the event of Early Termination during Part B, patients will be asked to complete an Early Termination Visit as soon as possible (see Section 6.2.33) and then return 28 ± 3 days after their last dose of IMP for a Post-Early Termination Safety Follow-Up Visit (Section 6.2.35). Safety data from Part B will be provided to the DSMB, at a frequency specified by its charter, for ongoing monitoring of safety and detection of any trends.

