3.1.2 Planned Number of Patients and Sites

Part A: Approximately 645 patients will be screened, assuming a 30% screen failure rate, to randomize 450 patients.

Part B: It is anticipated that 80% of the randomized patients (i.e., approximately 360 patients) will complete Part A and continue into the open-label phase.

Approximately 80 sites will participate in the study.

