5.8 Procedures for Monitoring Patient Compliance

After IMP is dispensed, at each subsequent study visit patients must return all used, unused, and partially used clinical IMP supplies (i.e., kits for Part A and bottles for Part B). Drug accountability must be done in the patient's presence in order to obtain explanations regarding discrepancies in compliance with the dosing regimen. Drug accountability must be recorded on the Drug Accountability Form. Upon completion of the patient's Visit 13 at Week 76 (or Early Termination Visit, whichever occurs first), the authorized study staff will enter the date of the last dose of IMP taken in the source documents and eCRF to register the end of treatment for that patient.

If a patient is found to be persistently noncompliant (≤ 80 to $\geq 120\%$ of the assigned dose), the Sponsor/Sponsor's designee, in conjunction with the investigator, will make a decision as to whether the patient should be discontinued from the study.

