6.2.18 Visit 7 (Week 24) (End of Double-Blind / Start of Open-Label Phase)

Note: Confirm the arrangement for laboratory sample pick-up on the day of the Week 24 visit with the courier (see Central Laboratory Procedures Manual).

Note: If a patient decides to withdraw from study at Week 24, their Week 24 visit will be an Early Termination Visit (see Section 6.2.32) and they will be asked to return for a Safety Follow-Up Visit within 28 ± 3 days (see Section 6.2.35).

- 1. Upon arrival, obtain samples for the following laboratory tests and record the date and time of collection:
 - a. Obtain first PK blood sample for plasma tozadenant concentration. Record the patient-reported date and approximate time when the patient took the most recent dose of IMP. Record the date and time of PK sample collection.

- For patients concomitantly taking pramipexole, plasma will also be analyzed for pramipexole plasma concentration using the same PK blood sample as drawn for tozadenant PK. Record the patient-reported date and approximate time when the patient took the previous dose of pramipexole prior to sampling. See Section 8.2.
- b. Hematology and chemistry (including liver function tests).
- c. TSH, free T3, and free T4.
- d. Urine sample for urinalysis.
- e. Verify method of contraception has not changed since the previous visit. For females of childbearing potential: urine pregnancy test.

- 2. Review the patient's PD diary recordings for the 3 consecutive days (i.e., 3 consecutive 24-hour periods) directly preceding this visit, and address any illegible or unclear entries.
- 3. Assess AEs by asking open-ended queries and record the assessments.
- 4. Record concomitant medication use; assess and record any changes to anti-PD medication dose or regimen.
- 5. Obtain and record BP and pulse measurements after at least 5 minutes supine rest and again after standing for approximately 1 and 3 minutes.
- 6. Obtain 12-lead ECG and ensure the ECG is collected at a time when the patient is not experiencing dyskinesia that would interfere with an adequate recording. Assess any changes from Baseline for clinical significance.
- 7. Obtain weight.
- 8. Record the date and approximate time of the most recent dose of levodopa taken prior to the UPDRS assessment.
- 9. Perform the following assessments in the ON state (items a, b and c):

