3 STUDY DESIGN

This is a Phase 3, international, multicenter, randomized, double-blind, placebo-controlled, parallel-group, 3-arm study with an open-label phase in levodopa-treated patients with PD experiencing end-of-dose "wearing-off". This study includes a Screening Period of up to 6 weeks that starts with a Screening Visit, a 24-week Double-Blind Treatment Period, a 52-week Open-Label Treatment Period, and a Safety Follow-Up Visit 4-weeks post-treatment. After providing written informed consent, patients will undergo screening evaluations. Patients must meet all inclusion criteria and none of the exclusion criteria, and they must successfully complete the diary training and achieve 80% overall diary concordance with the PD diary trainer/rater including at least 1 OFF interval to be considered for randomization. If preliminary eligibility is confirmed by the investigator and the Sponsor/Sponsor's designee, patients will then be scheduled for a Baseline Visit and will be required to return a valid set of Baseline diaries. Final eligibility will be determined at the Baseline Visit.

Eligible patients will be randomized in Part A to receive 1 of 2 tozadenant doses (60 mg BID or 120 mg BID) or placebo in a ratio of 1:1:1. Blinded IMP will be dispensed to patients at each study visit and will be taken BID (approximately 12 hours apart) for 24 consecutive weeks. Patients will return to the study site for evaluation at Weeks 2, 6, 12, 18, and 24. Patients will be contacted by telephone before the start of each 3-day PD diary completion period to be reminded to complete the diary for 3 consecutive days prior to their next scheduled visit. Unscheduled visits can be arranged as considered necessary by the investigator. In the event of Early Termination during Part A, patients will be asked to complete an Early Termination Visit as soon as possible and then return 28 ± 3 days after their last dose of IMP for a Post-Early Termination Safety Follow-Up Visit. Blinded safety data from the double-blind phase (Part A) will be provided to the Data and Safety Monitoring Board (DSMB), at a frequency specified by the DSMB charter, for ongoing monitoring of safety and detection of any trends. If requested by the DSMB, the DSMB statistician will provide unblinded safety data to the DSMB on a per needed basis, to enable a fully informed review.

The Schedule of Events/Evaluations for Part A is shown in **Table 3-1**.

Table 3-1: Part A – Schedule of Events/Evaluations

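### SAP 5.13 sets no end to the Part A TEAE window for patients who enter Part B, so open-label tozadenant events could be counted under placebo or 60 mg

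*SAP*

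**What the plan says.** SAP 5.13 defines TEAEs as events which "first occur or increase in severity or relationship to study drug after the first dose of study drug through the Post-dose Follow-up", and places that follow-up 28 ± 3 days after end of treatment. It does not define end of treatment and does not mention Part B. Its rules for incomplete dates have a lower bound (first dose) but no upper one: "Should the start date be missing then the AE will be considered treatment emergent".

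The follow-up visit does not exist for everyone in Part A. SAP 3 attaches it to early termination, with patients returning 28 ± 3 days after "their last dose of IMP for a Post-Early Termination Safety Follow-Up Visit". Protocol 6.2.18 adds those who withdraw at Week 24: "their Week 24 visit will be an Early Termination Visit". Protocol 3.1.2 expects that "80% of the randomized patients (i.e., approximately 360 patients) will complete Part A and continue into the open-label phase". For them Protocol 3.1 says that "The Safety Follow-Up Visit will occur 28 ± 3 days after the patient's last open-label dose of tozadenant".

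The switch has no gap. Under Protocol 6.2.18 the first open-label dose is taken at home on the evening of Visit 7. Protocol 3.1 starts all patients on 120 mg BID, and "those who received placebo will initiate open-label tozadenant".

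SAP 3.1.2 fixes the safety arm by the product received at first dose. SAP 9.7.1 tabulates TEAEs by that arm and for combined tozadenant, with no split by study phase.

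**The concern.** A single window with a 28-day tail suits a trial in which everyone stops drug. Here most patients go straight from double-blind to open-label drug, so for them the tail is time on tozadenant. A former placebo patient's first weeks on active drug could be tabulated as placebo experience. A former 60 mg patient's events on the open-label starting dose could be tabulated as 60 mg experience. The summaries affected include serious TEAEs, deaths and discontinuations due to adverse events.

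At stake are the placebo rate, the risk ratio and the dose comparison in the main safety tables. Two programmers following SAP 5.13 could also produce different tables.

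**Working it through.** **Inputs from the documents.** 450 patients randomized 1:1:1; 80% continue (Protocol 3.1.2); 24 weeks (168 days) double-blind; tail of 28 ± 3 days (SAP 5.13).

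**The plan's own figure.** 0.80 × 450 = 360, as stated. If equal across arms, 360 / 3 = 120 continuers and 150 − 120 = 30 early leavers per arm. Sample size and power are not affected.

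**Where the window ends for a continuer.** SAP 5.13 supports no clear answer.
- Read as Week 24, the window takes in 25 to 31 open-label days.
- Read as last dose of study drug, it would run on into Part B. That is how Protocol 5.8 uses the term: at Week 76 or Early Termination staff enter the "date of the last dose of IMP taken in the source documents and eCRF to register the end of treatment for that patient".
- Read through the Part A scope in SAP 1, events after the switch would be left out, but no date is given.

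The sizes below use the Week 24 reading.

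**Share of a continuer's window on open-label drug.** 28 / (168 + 28) = 14.3%; 25 / 193 = 13.0%; 31 / 199 = 15.6%.

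**Share of the placebo arm's window.** Assume the 30 leavers average 12 weeks on drug plus their own follow-up. With w = days / 7, share = 120w / [120(24 + w) + 30(12 + w)].
- 28 days: 480 / (3,360 + 480) = 480 / 3,840 = 12.5%.
- 25 days: 428.6 / 3,775.7 = 11.4%.
- 31 days: 531.4 / 3,904.3 = 13.6%.
- Leavers averaging 18 weeks, 25 days: 428.6 / 3,955.7 = 10.8%. Leavers averaging 6 weeks, 31 days: 531.4 / 3,724.3 = 14.3%.

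**Effect on a comparison.** The documents give no event rates. Assume 24-week risks of 5% on placebo and 15% on tozadenant, a constant hazard, and leavers at full 24-week risk. With a 28-day tail:
- Placebo: 0.8[1 − 0.95 × 0.85^(4/24)] + 0.2 × 0.05 = 7.03%.
- Tozadenant: 0.8[1 − 0.85^(28/24)] + 0.2 × 0.15 = 16.82%.
- Risk ratio: 15 / 5 = 3.0 becomes 16.82 / 7.03 = 2.39 (2.44 at 25 days, 2.35 at 31).
- Risk difference: 10.0 becomes 9.8 points.
- Extra placebo patients with the event: 150 × (0.0703 − 0.05) = 3.0.

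**Sensitivity to leavers.** If leavers are at risk for 12 weeks on drug and then 4 weeks at the placebo hazard, the risks without open-label time are 4.67% and 13.72% (ratio 2.94, difference 9.05). With it they are 6.70% and 15.54% (ratio 2.32, difference 8.83).

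**Sensitivity to early onset.** Let a fraction f of the 10-point drug excess fall in the first 4 weeks on drug, with rates added linearly. Placebo = 5 + 0.8(10f + 5 × 4/24). Tozadenant = 15 + 0.8(10(1 − f) × 4/20 + 5 × 4/24).
- f = 0.25: 7.7% against 16.9%, ratio 2.2, difference 9.2 points.
- f = 0.5: 9.7% against 16.5%, ratio 1.7, difference 6.8 points.

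**The case against.** The strongest reply is scope. SAP 1 says the plan covers data collected under Part A and that a Part B SAP will follow; the safety objectives in SAP 2.4 are headed Part A. SAP 5.13 names a visit that continuers do not have in Part A, so the tail can be read as applying only to patients who do. SAP 7.2 and SAP 8 provide a blinded review before lock, where a cut-off could be agreed, and all adverse events are listed. On the constant-hazard figures the risk difference hardly changes, and the larger shifts depend on an assumed early onset.

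Much of this stands. It makes the error avoidable, and it means misattribution is possible rather than certain. It does not repair the rule: no sentence gives an adverse-event cut-off, and the scope statement does not settle same-day, partly dated or undated events at the switch.

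A reader might infer from Protocol 5.8 that the Part A window runs through the whole of Part B. The documents do not support sizing the problem that way. SAP 8 ties cleaning, lock and unblinding to completion of Part A, and nothing suggests that the lock would wait for open-label follow-up.

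A reader might also extend the point with equal force to laboratory data, since the worst-post-baseline displays and the last-on-treatment ANOVA in SAP 9.7.3 state no Part A limit. That is weaker. The by-visit laboratory summaries refer to the scheduled visits in Table 1, and in a Part A plan, on treatment naturally means double-blind treatment. The ECG summaries in SAP 9.7.10 are by Part A visit.

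**Conclusion.** The point holds as a gap in a stated rule that gives a wrong result if applied literally. With end of treatment read as Week 24, about 4 weeks of open-label exposure per continuer, or about 12.5% of placebo-arm window time (10.8% to 14.3% over the assumptions tried), could be booked under placebo, with the corresponding exposure in the 60 mg arm booked under 60 mg. The likely direction is a higher placebo TEAE rate and a risk ratio closer to 1, about 3.0 to 2.4 in the illustration. The risk difference is nearly unchanged unless drug-related events cluster early.

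This rests on 80% continuation being equal across arms and on assumed leaver times, event rates and hazards. It does not show that the tables will be wrong: an analyst who follows the Part A scope would exclude these events. The change should be made, but it does not touch the efficacy analysis.

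**What to change.** Amend SAP 5.13 before unblinding:
- For patients entering Part B, close the Part A TEAE window at the first open-label dose. The Visit 7 steps do not list recording that dose time, so where it is missing use the Visit 7 or dispensing date with a stated convention for same-day events (for example, count them as Part A).
- Keep the 28 ± 3 day window for patients who do not enter Part B.
- Give the partial- and missing-date rules the same upper bound: treat an event as Part A unless the available date information places it after the switch.
- Report later events under Part B.

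For consistency, state in SAP 9.7.3 that the worst-post-baseline shift and plots and the last-on-treatment ANOVA use double-blind data only.

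The cost is one or two SAP sentences, a date flag and a convention for a few switch-day events. Some undated events that began in Part B may stay in Part A, because the documents do not show a field that would place them. The SAP was written against Amendment 1 and the protocol is now at Amendment 3, so the change can go into an SAP update.

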6 INTERIM ANALYSES

There is no planned interim analysis for this study.

7 DATA REVIEW

7.1 Data Handling and Transfer

Data are entered electronically into a clinical database built by << Provider>> and exported as SAS® datasets. SDTM and ADaM datasets will be generated following the Clinical Data Interchange Standards consortium (CDISC) conventions. Data analyses including summary tables, figures, and data listings are produced using SAS®.

Clinical laboratory results and normal ranges will be provided as SAS datasets from the central clinical laboratory vendor. Protocol deviations and violations (PDVs) will be identified by the Sponsor prior to database lock and flagged for exclusion from the ES population.

CONFIDENTIAL

Randomization data will be imported into the dataset after database lock at the time of unblinding.

7.2 Data Screening

There will be one database freeze during which the data will be exported and the TLFs generated based on this data export. The TFLs will be reviewed by the Sponsor in a blinded data review meeting to identify any final data issues, determine major/minor violations and evaluable subjects analysis set and seek corrections prior to database lock. The Sponsor must approve database lock.

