5.11 Blinding

During Part A, an IXRS will be used for assigning eligible patients to a treatment regimen based on a predetermined production randomization and/or packaging schedule. The randomization schedule will be produced by a biostatistician. The IXRS will generate individual assignments for patient IMP kits according to the visit schedule. The identity of the dosing group assignments will be concealed by identical appearance, packaging, labeling, and schedule of administration. The randomization code will be kept strictly confidential until the time of unblinding and will not be broken without authorization. Blinding will not be compromised for individuals involved with operational aspects of the study including bioanalysis of samples for study drug concentrations, as well as individuals involved with the planning and conduct of the final statistical analyses.

Blinded safety data from the double-blind phase (Part A) will be provided to the DSMB, at a frequency specified by the DSMB charter, for ongoing monitoring of safety and detection of any trends. If requested by the DSMB, the DSMB statistician will provide unblinded safety data to the DSMB, on a per needed basis and in accordance with the DSMB charter, to enable a fully informed review.

The study will be open-label during Part B.

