3.1.4 Per Protocol Set (PPS)

The PPS will consist of all randomized patients who have an efficacy evaluation (number of hours per day spent in the OFF state while awake) at Week 24 and have no major protocol deviations/violations. In addition, subjects randomized to tozadenant must have measureable plasma concentrations at each post-baseline visit for the subject to be considered in the PPS (i.e. not have any below-the-limit-of-quantification result from the bioanalysis at any post-baseline visit). This will not exclude subjects who had missing samples or values, for any reason, from the analysis. (For example, instances where the analytical lab was unable to obtain a result from a sample they received, or no sample was received, or the bioanalytical results were considered invalid.)

Patients will be accounted for in the treatment group to which they were originally randomized.

Summaries and/or analyses of the primary endpoint and four key secondary endpoints will be done in the PPS.

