9.6.7 Tozadenant Plasma Concentrations

During Part A of the study, blood samples will be collected for determination of plasma tozadenant concentrations at baseline before dosing, at weeks 2, 6 12, 18 and 24 (end of dosing). In addition, samples may be taken at an unscheduled visit and at an early termination visit.

Plasma concentration data will be presented for all subjects in the safety population by treatment group, including placebo. In all calculations, including placebo-group subjects, zero (0 ng/mL) will be substituted for concentration below the quantification limit (BLQ; equivalent to <5 ng/mL) of the assay.

Elapsed time between dosing and plasma sampling will not be tightly controlled and is expected to vary considerably between patients. Summary statistics for tozadenant blood concentrations (number of sample analyzed, number of BLQ values, minimum, and maximum) will be presented by sampling occasion. For treatment visits when 2 consecutive plasma samples are analyzed (weeks 2 and 24), the 2 values will be presented separately.

All data collected on the tozadenant blood concentrations will be included in the data listings.

Separate population analyses on the data from this study alone or combined with data from other studies as deemed appropriate may be performed and reported separately.

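### The SAP does not keep tozadenant plasma levels out of the TFLs reviewed before lock, and its PPS drug-level rule cannot be settled at a blinded meeting

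*SAP*

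**What the plan says.** **Timing and content of the review (SAP 7.2).** "There will be one database freeze during which the data will be exported and the TLFs generated based on this data export". On the review itself: "The TFLs will be reviewed by the Sponsor in a blinded data review meeting to identify any final data issues". The meeting is also to "determine major/minor violations and evaluable subjects analysis set and seek corrections prior to database lock".

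**What is held back (SAP 7.1).** Randomization data enter the dataset after lock, at unblinding. No other data are named as withheld.

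**What the listings contain (SAP 9.6.7).** "All data collected on the tozadenant blood concentrations will be included in the data listings". Placebo patients are covered too: in calculations, "including placebo-group subjects, zero (0 ng/mL) will be substituted for concentration below the quantification limit", which is 5 ng/mL. On sampling time, "Elapsed time between dosing and plasma sampling will not be tightly controlled and is expected to vary considerably between patients".

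**The per-protocol rule (SAP 3.1.4, and Protocol 11.1).** Besides a Week 24 evaluation and no major deviation, "subjects randomized to tozadenant must have measureable plasma concentrations at each post-baseline visit for the subject to be considered in the PPS". Missing samples do not exclude; any result below the limit does. SAP 9.2 has the sponsor flag PPS exclusions for deviations before lock.

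**The general commitment (Protocol 5.11).** "The randomization code will be kept strictly confidential until the time of unblinding and will not be broken without authorization". The same section says that blinding will not be compromised for people in operational roles, naming bioanalysis of drug concentrations, or for those planning and conducting the final analyses.

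**The concern.** A tozadenant concentration comes close to being a treatment code. A quantifiable value can only come from a patient who took active drug; an unbroken run of values below the limit points to placebo. A by-patient listing shows this even if the randomization file is locked away or dummy codes are used.

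The SAP also gives the reviewers a reason to look at drug levels, because the drug-level rule is part of the PPS definition and the meeting is told to settle the evaluable set. Yet the rule applies only to patients randomized to tozadenant, and arm is unavailable at that point.

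At stake is whether data queries, the grading of deviations as major or minor, and PPS membership are decided without knowledge of treatment. The PPS carries a sensitivity analysis of the primary endpoint and of the key secondary endpoints.

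**Working it through.** The plan gives no figure of its own on this point, so the check is a comparison of sections followed by a calculation of what a concentration listing would reveal.

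**1. Can the steps all be followed while blind?**
- (a) The evaluable set is determined at the pre-lock meeting (SAP 7.2).
- (b) The PPS needs plasma level and randomized arm (SAP 3.1.4).
- (c) Arm is available only after lock (SAP 7.1).

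SAP 3.1 defines no evaluable set. I read it as the PPS, because SAP 7.1 and SAP 9.2 describe the same flagging step and differ only in the set they name. On that reading (a), (b) and (c) cannot all hold. If the rule were applied without arm, the placebo group, which should be below the limit throughout, would be flagged for exclusion. If plasma level stood in for arm, an active patient who never showed drug would look like placebo and stay in. This conflict does not depend on when the concentrations are loaded.

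**2. Samples per patient.** Protocol 8.1 schedules 2 at Week 2, 1 each at Weeks 6, 12 and 18, and 2 at Week 24: 2 + 1 + 1 + 1 + 2 = 7 post-baseline for a Part A completer.

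**3. Active versus placebo, if the listing is seen.** The documents give no rate of results below the limit in the active arms, so two assumptions are tried.

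*Independent samples, each below the limit with probability q.* P(all 7 below the limit, given active) = q^7.
- q = 0.05: 8 × 10⁻¹⁰
- q = 0.30: 0.0002

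A patient who leaves with only the two Week 2 results gives q² = 0.0025 to 0.09, so early leavers are less clear.

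*A fraction f of active patients always below the limit, for instance through non-adherence.* With 1:1:1 allocation, the share of patients correctly read as active or placebo is 1/3 + (2/3)(1 − f).
- f = 0.02: 0.987, or 300 × 0.02 = 6 of 450 misread
- f = 0.10: 0.933, or 300 × 0.10 = 30 of 450 misread

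**4. Exact arm.** Guessing blind names the arm correctly 1/3 of the time. Knowing only active versus placebo raises this to 1/3 + (2/3)(1/2) = 2/3. To illustrate dose, assume log-normal levels proportional to dose, with total coefficient of variation CV, so that σ = √ln(1 + CV²). One sample then classifies 60 mg versus 120 mg correctly with probability Φ(½ ln 2 / σ).

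| CV | Correct |
|---|---|
| 30% | 88% |
| 60% | 73% |
| 100% | 66% |
| 150% | 63% |

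Uncontrolled sampling times push towards the lower rows. Repeated samples would help somewhat, by an amount that the documents do not allow to be computed.

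**The case against.** The strongest reply is that exposure is inferred. SAP 7.2 does not list what is exported. SAP 7.1 names the clinical database and the central clinical laboratory as sources, not the bioanalytical results, and no section says when those are loaded. The output shells and the list of listings are in later or separate documents. This stands: one may not assert that the reviewed outputs contain drug levels. It does not remove the point that nothing excludes them, and it does not touch the sequencing conflict in the PPS rule.

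The second reply is Protocol 5.11, which does extend to operational roles and names bioanalysis. It is a real commitment and plausibly covers pre-lock review. It states an outcome, however, and gives no procedure for concentration data or for this meeting.

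Third, the drug-level rule is a separate, mechanical criterion that presupposes arm, so it may have been meant for use after unblinding. That is sensible, but SAP 7.2 settles the evaluable set before lock and makes no such split.

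Fourth, discretion is limited. Protocol 11.7 wants deviation criteria defined before unblinding, as far as feasible without looking at the data, and applied by algorithm where possible. Protocol 10.3 requires reasons for eCRF changes and an audit trail. These reduce the risk without removing it.

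**Conclusion.** The point holds as a gap in procedure together with a conflict of sequence. The PPS cannot be completed at a blinded pre-lock meeting, whatever the timing of the concentration data. If those data are in the freeze outputs, active versus placebo could be inferred for nearly all patients with results: about 93% to 99% if 2% to 10% of active patients are always below the limit, and more if results below the limit are scattered. The size of any resulting bias cannot be computed from the documents. No sample-size or power figure changes.

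Three stronger readings are tempting and are not supported:

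- *Each patient's arm could be read.* With three arms and uncontrolled sampling times, the two doses separate only imperfectly.
- *The blinded review under ICH E9 (SAP 8) is false as described.* As written, the review precedes unblinding and the codes are withheld. What is missing is a safeguard.
- *The primary analysis is directly compromised, including through country pooling.* The primary set depends on dosing and valid diaries, diary validity is a count of invalid entries, and pooling is triggered by small patient numbers in a country, which drug levels do not inform.

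The main exposure is therefore data queries, deviation grading and the PPS sensitivity analysis.

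**What to change.** - **SAP 7.1 and 7.2:** state that tozadenant concentrations are excluded from the freeze export and from all TFLs produced before lock, and are merged after lock together with the randomization data. Name the PPS in place of the undefined evaluable set, if that is what is meant.
- **SAP 3.1.4 and 9.2:** settle the deviation-based PPS exclusions at the blinded review. Apply the drug-level criterion after unblinding, by a program specified in advance, with no discretion.

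The cost is SAP wording and one prespecified program. Endpoints, data collection and sample size are unaffected. The one drawback is that the final PPS count is known only after unblinding.
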